4. TREATMENT OF SUBJECTS

Nonsurgical treatment

The nonsurgical treatment policy consists of relative rest (stop exercise, bed rest), wound care with sterile bandages and pressure bandage; hospital admission may be considered. On day 16 wound classification, clinical examination and CRP are performed. In case of persistent leakage at day 16, a DAIR according to study protocol is advised on days 17-20.

Surgical treatment

DAIR on day 10. DAIR is meant to clean the prosthesis and the wound in order to conquer the possibility of infection. DAIR consists of opening the wound, taking one culture from the fluid deep to the fascia and at least four deep-tissue cultures: two synovial and at least one around both components of the joint prosthesis. Only after taking cultures antibiotics are started and the hematoma and necrosis excised. Mobile parts (e.g. tibial insert, femoral head) are exchanged to make room for optimal debridement. The wound is lavaged thoroughly with 3-6 litres of saline. It is advised to use scrub sponges to mechanically clean all visible prosthetic parts. Povidone iodine solution or chlorhexidine solution may be used.

4.1 Investigational product/treatment

NA

4.2 Use of co-intervention (if applicable)

NA

4.3 Escape medication (if applicable)

NA

5. INVESTIGATIONAL PRODUCT

NA

6. NON-INVESTIGATIONAL PRODUCT

NA

7. METHODS

7.1 Study parameters/endpoints

7.1.1 Main study parameter/endpoint

The primary clinical outcome is the percentage of prevented revision for PJI within one year and the involved costs.

7.1.2 Secondary study parameters/endpoints (if applicable)

Study parameters are wound class, temperature, CRP, culture results, second surgery. Patient parameters include BMI, ASA, smoking, medication.

Disease specific and general health related quality of life. The short HOOS and KOOS and the Oxford Hip and Knee Score will be used as disease-specific outcome instruments. The EQ-5D-5L will be used as a generic health-related quality of life questionnaire. To get an impression of pain an NRS will be used. All questionnaires are recommended by the Netherlands Orthopaedic Association (NOV) and are included in the standard Patient Reported Outcome Measure (PROM) for both TKA and THA patients. In Dutch hospitals it is standard procedure that patients fill in these questionnaires preoperatively and at 3, 6 and 12 months postoperatively.

7.1.3 Other study parameters (if applicable)

COST-EFFECTIVENESS ANALYSIS (CEA):

The cost effectiveness analysis typically integrates two quantities: 1. the additional costs (or savings) of the surgical protocol (DAIR) compared with the nonsurgical treatment, and 2. the additional health benefits. Based on these 2, a third metric is calculated: The Incremental Cost Effectiveness Ratio (ICER), which is the difference in costs, divided by the difference in effects.

Cost analysis

In the CEA, costs will include primary treatment (including home care) and health care associated with revision for infection in the first year (estimated from patient charts). Productivity losses will also be included. All items of resource use will be collected at the patient level, using CRFs and patient Questionnaires (iMCQ and iPCQ (www.imta.nl)). Estimated productivity costs will include short-term losses due to hospitalization and lifelong losses due to mortality (using general Dutch labor participation and income data). Health care will be valued using standard prices [zorginstituut Nederland, 2015], with time and travel costs included in the CUA. Productivity losses will be valued using both the friction-cost method (primary analysis) and the human-capital method.

Patient outcome analysis

In the CEA, patient outcome will be measured by the incidence of revision for infection. In the CUA, in the trial-based analysis the impact on QALY loss will rely on trial results based on the EQ-5D-5L. The quality of life assessments in our own patients will be used to calibrate the literature estimates to our specific patient population.

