9.3 Other study parameters

In the economic evaluation, primary aim will be to estimate the societal costs of the surgical strategy with a DAIR on day 10, and compare this to the costs of the nonsurgical treatment strategy. Secondary aim will be to estimate the cost effectiveness of the surgical strategy compared to nonsurgical treatment (from a societal perspective), based on the primary measure of effectiveness (number of infections prevented). Finally, a costs utility analysis will be performed based on EuroQol (5D-5L)-defined utilities.

Results of the cost effectiveness analysis will display the additional costs or savings with the surgical strategy in order to prevent one additional patient with an infection compared to nonsurgical treatment. Results of the cost utility analysis will display the additional costs or savings with the surgical strategy in order to gain one quality-adjusted life year (QALY) compared to nonsurgical treatment.

The time horizon of this study will be 12 months, therefore the analysis will not include discounting of costs and effects. Bootstrap resampling will be performed on the cost, and on the cost and effect pairs in order to calculate confidence intervals. Cost effectiveness acceptability curves will also be plotted, to estimate the probability of the surgical strategy being more cost-effective than the nonsurgical treatment strategy, for different amounts of money that a decision-maker may be willing to pay for one additional unit of effect (infection avoided, QALY).

BUDGET IMPACT ANALYSIS (BIA)

General considerations

A budget impact analysis will be conducted from a healthcare perspective as well as from a health insurance perspective. The basic case scenario will focus on a one-year impact at the national level. Scenario analysis will adopt a four-year horizon.

Cost analysis

A budget impact analysis (BIA) will be conducted to inform decision-makers about the financial consequences of the adoption and diffusion of the surgical strategy (DAIR) in

the Dutch healthcare system. The BIA will use a deterministic model. The model input parameters will be mainly based on results of the current clinical- and cost-effectiveness study and available literature. For the BIA, no additional patient level data will be collected.

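### Lifelong productivity losses from death do not fit an undiscounted 12-month economic evaluation or the friction-cost method named as primary

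*Protocol*

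**What the plan says.** Protocol section 7.1.3 (Cost analysis) lists two components of productivity cost: short-term losses from hospitalisation, and "lifelong losses due to mortality (using general Dutch labor participation and income data". The next step is valuation: "Productivity losses will be valued using both the friction-cost method (primary analysis) and the human-capital method". Health care cost in the same section is bounded in time: "health care associated with revision for infection in the first year (estimated from patient charts".

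Effects are also described in 7.1.3. For the cost-effectiveness analysis, "In the CEA, patient outcome will be measured by the incidence of revision for infection". For the cost-utility analysis, "in the trial-based analysis the impact on QALY loss will rely on trial results based on the EQ-5D-5L". A further sentence says that the trial's own quality-of-life assessments "will be used to calibrate the literature estimates to our specific patient population".

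Section 9.3 then fixes the frame: "The time horizon of this study will be 12 months, therefore the analysis will not include discounting of costs and effects". It also ranks the economic aims: the "primary aim will be to estimate the societal costs of the surgical strategy with a DAIR on day 10" and compare them with those of nonsurgical treatment. Cost-effectiveness and cost-utility follow after that.

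**The concern.** The protocol fixes two rules that collide. A loss that runs for the rest of a working life lies outside a 12-month horizon, and the reason given for not discounting does not cover it. An analyst who follows 7.1.3 literally enters many years of undiscounted earnings for each death. An analyst who follows 9.3 stops at 12 months. Each can cite the protocol.

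The friction-cost method adds a second difficulty. It counts production loss only until the worker is replaced, so it leaves no room for a lifelong loss. The protocol does not say that the lifelong component is meant for the human-capital valuation alone.

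At stake is the match between the two halves of the cost-effectiveness ratio. In the human-capital analysis the cost of a death could run for decades, while its effect is counted, as far as the protocol states, over one year. A single large individual cost also behaves badly under the bootstrap planned in 9.3. The cost result and the acceptability curves could then depend on the age and arm of one or two patients who die.

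**Working it through.** **Inputs from the protocol**
- Revision for PJI: 20% without surgery, halved by DAIR, so 10% (section 3.4).
- Cost of a revision for PJI: about EUR 30,000 (Summary and section 1).
- Arm size: 155, or 194 after 20% dropout (section 3.4).

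**Reproducing the protocol's own figures**
- Sample size, one-sided 5%, 80% power, unpooled variance: (1.645 + 0.842)² × (0.20 × 0.80 + 0.10 × 0.90) / 0.10² = 154.6, so 155 per arm.
- Dropout: 155 / 0.80 = 193.75, so 194 per arm.
- National cost: 200 × EUR 30,000 = EUR 6,000,000, as stated in section 1.

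**Yardstick: the gross revision saving implied by the design**
- (0.20 − 0.10) × EUR 30,000 = EUR 3,000 per patient.
- Over one arm: 194 × EUR 3,000 = EUR 582,000.

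**Assumptions that the protocol does not supply**
- Expected earnings after allowing for labour participation: EUR 10,000 to 40,000 a year.
- Remaining working years: 2 to 30.
- Friction period: 2 to 6 months.

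**Effect of one death on mean cost in its arm**

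Loss = annual earnings × years. Per patient = loss / 194. Share = per patient / 3,000.

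| Rule for the death | Loss (EUR) | Per patient (EUR) | Share of EUR 3,000 |
|---|---|---|---|
| Lifelong, 10,000 × 2 years | 20,000 | 103 | 3% |
| Lifelong, 20,000 × 5 years | 100,000 | 515 | 17% |
| Lifelong, 20,000 × 20 years | 400,000 | 2,062 | 69% |
| Lifelong, 20,000 × 30 years | 600,000 | 3,093 | 103% |
| Lifelong, 40,000 × 20 years | 800,000 | 4,124 | 137% |
| Lifelong, 40,000 × 30 years | 1,200,000 | 6,186 | 206% |
| Full 12 months, 10,000 to 40,000 | 10,000 to 40,000 | 52 to 206 | 1.7% to 6.9% |
| Friction, 10,000 for 2 months | 1,667 | 9 | 0.3% |
| Friction, 40,000 for 6 months | 20,000 | 103 | 3.4% |

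A worked middle case assumes EUR 35,000 income and 65% participation, so EUR 22,750 a year:
- 7 years: 159,250 / 194 = EUR 821 per patient (27%).
- 17 years: 386,750 / 194 = EUR 1,994 per patient (66%).
- Cut at 12 months: 22,750 / 194 = EUR 117 per patient.
- Three-month friction period: 5,688 / 194 = EUR 29 per patient.

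A lifelong loss exceeds the whole gross saving only above EUR 582,000. For a patient past working age it is close to zero.

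**Net contrast.** The yardstick is gross, because the added cost of DAIR is not given. If DAIR added an assumed EUR 2,000 per patient, the net saving would be EUR 1,000, and one death of 194 × 1,000 = EUR 194,000 would equal it.

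**Effect side.** Over 12 months one death costs at most 1 QALY, or 1/194 = 0.005 per patient.

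**Discounting.** At an assumed 4% a year, the lifelong sum falls by 11% over 5 years, 19% over 10 years and 42% over 30 years.

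**Bootstrap.** If 194 patients are resampled within the arm, one given patient is absent from (193/194)^194 ≈ 37% of resamples, is drawn once in about 37%, and is drawn twice or more in the remaining 26% or so.

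**The case against.** The strongest reply is that friction costing is the primary valuation. Section 7.1.3 can be read as first naming the sources of loss (hospitalisation, mortality) and then valuing them in two ways. On that reading the friction valuation trims the mortality component by itself, and the lifelong loss appears only in the second method. This largely stands. It makes the clash with friction costing a matter of loose drafting and confines the material effect to the human-capital analysis. It does not settle the horizon, because section 9.3 applies 12 months and no discounting to the evaluation without exempting the human-capital analysis.

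A reader might infer that one death would overwhelm the societal cost comparison that 9.3 makes the primary economic aim. The documents do not support that. Under friction costing the shift is a few per cent at most. Even under lifelong costing, the two worked middle cases stay below the gross saving.

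A reader might also take it as stated that QALYs stop at one year. That is inferred from the 12-month horizon and the trial-based EQ-5D-5L. The sentence on calibrating literature estimates may point to a modelled component, but no longer horizon for effects is given. Nor can deaths be called unrelated to the allocated strategy: the protocol gives no mortality rate, and section 1 lists anaesthetic and surgical risks of DAIR.

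Finally, discounting alone changes little for patients near retirement. That is true. The larger issue is the mismatch of horizons.

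**Conclusion.** The point holds as an internal contradiction with a bounded consequence. Lifelong mortality losses cannot coexist with a 12-month horizon that is used to justify no discounting, and the word *lifelong* does not belong with a friction-cost primary analysis.

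The size rests on assumed earnings, working years and friction period, since the protocol gives none of these and no age distribution. It also uses a gross yardstick that leaves out the cost of DAIR. Within those assumptions, one working-age death could materially distort the human-capital contrast. The primary valuation is exposed only if the lifelong wording is carried into it by mistake.

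The clinical comparison of revision rates, the sample size and the data collection are unaffected. This should be corrected, but it does not threaten the trial's main clinical result.

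**What to change.** In Protocol section 7.1.3, remove the lifelong component from the 12-month trial-based analysis and state the limit for each method:
- friction-cost (primary): mortality losses counted only over the friction period, within the 12 months;
- human-capital: mortality losses counted only for the remainder of the 12 months.

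If lifelong human-capital losses are still wanted, report them in a separate scenario with a stated discount rate and a QALY horizon that covers the same deaths over the same years. Add to section 9.3 that the 12-month, undiscounted frame applies to the trial-based analysis and not to that scenario. In the same edit, say what the calibrated literature estimates are for and over what horizon. Carry the wording into the statistical or economic analysis plan if there is one, before cost data by arm are seen.

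The cost is a change of wording, with no new data. The downside is that the human-capital mortality cost becomes smaller, and the long-run production loss from a death is then visible only in the separate scenario.

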7.2 Randomisation, blinding and treatment allocation

A randomisation on patient level will be executed. The randomization procedure will be designed and implemented by the Trial Coordination Center (TCC) UMCG using the validated web-based system ALEA. Each user will receive an individual login code with which to randomize patients. The web application will return the allocated treatment. As a confirmation the web application will also send an e-mail to selected users containing the randomization information. The system is online 24 hours a day, 7 days a week.

7.3 Study procedures

Nonsurgical treatment

Patients in the nonsurgical treatment group will be treated following a nonsurgical treatment policy. This policy consists of relative rest (stop exercise, bed rest), wound care with sterile bandages and pressure bandage; hospital admission may be considered. On day 16 wound classification, clinical examination and CRP are performed. In case of persistent leakage at day 16, a DAIR according to study protocol is advised on days 17-20.

Surgical treatment

DAIR on day 10. DAIR is meant to clean the prosthesis and the wound in order to conquer the possibility of infection. DAIR consists of opening the wound, taking one culture from the fluid deep in the fascia and at least four deep-tissue cultures: two synovial and at least one around both components of the joint prosthesis. Only after taking cultures are antibiotics started and the hematoma and necrosis excised. Mobile parts (e.g. tibial insert, femoral

head) are exchanged to make room for optimal debridement. The wound is lavaged thoroughly with 3-6 litres of saline. Scrub sponges are used to mechanically clean all visible prosthetic parts. Povidone iodine solution or chlorhexidine solution may be used as additional intraoperative antiseptic.

7.4 Withdrawal of individual subjects

Subjects can leave the study at any time for any reason if they wish to do so without any consequences. The investigator can decide to withdraw a subject from the study for urgent medical reasons.

7.4.1 Specific criteria for withdrawal (if applicable)

NA

7.5 Replacement of individual subjects after withdrawal

Subjects who withdraw will be replaced in order to maintain a sufficient sample size, although a drop-out rate of 20% has been accounted for.

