Revision surgery for PJI has major implications for a patient's quality of life (multiple surgeries, longer operating times, increased blood loss and more complications, lengthy hospital stays and long-term antibiotic treatment). In addition, the costs associated with revision surgery are high (\pm € 30,000) [Kurtz, Bozicz, Vanhegan 2012]. In the Netherlands, revision surgery within one year is necessary in more than 600 patients (0.9% TKA and 1.4% THA). According to the "Landelijke Registratie Orthopedische Implantaten" (LROI), infection is the reason for revision within one year in 25.8% TKA and 12.3% THA revision cases. A Danish register study evaluated underreporting of infection as reason for revision and found it to be at least 40% [Gundtoft 2015]. This leads to the assumption that at least 1/3 of revisions within one year are related to PJI (200 patients). The associated costs for revision surgery for PJI within one year are therefore estimated at € 6,000,000 (200 x € 30,000). However, the number of revisions for PJI is probably much higher with longer follow-up, as many PJI cases are caused by lower-virulence bacteria. PJI within two years is therefore still generally considered to be related to the primary surgery. This is expressed in the LROI figures for revisions for PJI: in 2014 there were 2541 TKA and 3574 THA revisions with infection as reason for revision, 15% and 11% respectively, on a yearly base. Considering 40% underreporting, it can be estimated that approximately 1064 patients need revision surgery for PJI, of whom at least 200 are operated within the first year of index surgery and the other 800 after the first year. So it can be concluded that the actual rate of PJI is probably largely underestimated, as was also discussed for the Danish National Hip register [Gundtoft 2015]. This underestimation will also be present for the Dutch Arthroplasty register (LROI), despite its completeness of over 97% [Steenbergen 2015].

OBJECTIVES

Primary Objective:

To determine the clinical and cost effectiveness of surgical treatment (DAIR day 10) versus nonsurgical treatment in patients with wound leakage after TKA/THA.

Secondary Objective(s):

To compare the impact of surgical treatment (DAIR day 10) with nonsurgical treatment on disease-specific and general health-related quality of life.

HYPOTHESIS:

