3.4 Sample size calculation

The power analysis is based on the assumption that, in patients experiencing persistent wound leakage at day 9, PJI eventually will develop and will necessitate revision surgery in 20% of cases. It is hypothesized that surgical intervention (DAIR day 10) will prevent 50% of PJI and consequently 50% of revision surgery for PJI in comparison to the non surgical intervention. In order to detect this 50% difference with 80% power at a significance level of 0.05, 155 patients are needed in the surgical group and 155 in the nonsurgical group. With an expected dropout rate of approximately 20% a sample size of 194 patients per group is needed (total N=388).

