7.6 Follow-up of subjects withdrawn from treatment

These subjects will be followed-up by usual care protocols.

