9. STATISTICAL ANALYSIS

Statistical analyses will be performed with the help of IBM SPSS statistics 22. An intention to treat analyses will be performed. For all analyses a one-tailed significant level of $p < 0.05$ is considered to be statistically significant

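### The replacement rule in Section 7.5 covers dropout a second time, and Section 7.6 does not secure the one-year outcome of withdrawn patients

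*Protocol*

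**What the plan says.** Section 3.4 assumes that, without surgery, "PJI eventually will develop and will necessitate revision surgery in 20% of cases", and that DAIR "will prevent 50% of PJI and consequently 50% of revision surgery for PJI". It plans "with 80% power at a significance level of 0.05" and arrives at 155 patients per group. It then adds: "With an expected dropout rate of approximately 20% a sample size of 194 patients per group is needed", which makes 388 in total.

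Section 7.4 lets patients leave at any time for any reason and lets the investigator withdraw them for urgent medical reasons. Section 7.4.1 gives no specific criteria. Section 7.5 states: "Subjects who withdraw will be replaced in order to maintain a sufficient sample size, although a drop-out rate of 20% has been accounted for". Section 7.6, on patients withdrawn from treatment, consists of one sentence: "These subjects will be followed-up by usual care protocols".

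Section 9 states: "An intention to treat analyses will be performed". It sets a one-tailed 0.05 level for all analyses.

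**The concern.** There are two linked problems.

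First, Section 7.5 concedes that dropout is already in the sample size and still adds replacements. It sets no limit on them, so the number of patients to be randomised is no longer fixed.

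Second, under intention to treat a randomised patient cannot be replaced. The patient stays in the allocated arm, and what is needed is the outcome. Replacing someone to maintain the sample size makes sense only if that person has dropped out of the count. Section 7.6 does not correct this impression, because it never says that one-year revision status is obtained for patients who stop treatment. Sections 7.4 to 7.6 also do not distinguish stopping the allocated treatment from leaving the study.

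At stake is the primary comparison. One arm is an operation and the other is rest and wound care. The randomisation system returns the allocation to users (Section 7.2), no blinding is described, and the patient code contains the study group (Section 11.1). Withdrawal can therefore depend on arm and prognosis. New patients restore the numbers but not the lost outcomes.

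**Working it through.** **Inputs.** Section 3.4 gives a nonsurgical rate of 20%, a surgical rate of 10% (a 50% reduction), 80% power, alpha 0.05 and 20% dropout. The one-tailed level comes from Section 9, because Section 3.4 does not state sidedness.

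**1. The plan's own figures.** With the unpooled normal approximation, one-sided:

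n = (1.6449 + 0.8416)² × (0.20 × 0.80 + 0.10 × 0.90) / 0.10² = 6.183 × 25 = 154.6, so 155 per group.

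Allowing for dropout, 155 / 0.8 = 193.75, so 194 per group and 388 in total. Both figures reproduce exactly.

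**2. Is replacement needed?** 194 × 0.8 = 155.2, so 155 per group remain after the assumed loss. The pooled-variance formula gives 79.6% one-sided power with 155 per group, in effect the planned 80%. At the loss the protocol expects, replacement adds nothing that the plan requires.

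**3. What replacement does to the number randomised.**

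- Each withdrawal replaced once: 194 + 0.2 × 194 = 232.8, about 233 randomised per group; 232.8 × 0.8 = 186 complete.
- Replacement until 194 per group complete: 194 / 0.8 = 242.5, so 243 per group and 486 in total, which is 98 more than 388. One-sided power is then 87.0%.

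The protocol does not say which of these is meant.

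**4. What lost outcomes could do.** The protocol gives no withdrawal rate by arm and no risk among withdrawn patients, so the figures below are assumptions that show a range.

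Suppose the true risk is 20% in both arms, a share d of the surgical arm withdraws with risk w, and their outcomes are not in the analysis. The surgical rate seen is r = (0.20 − d × w) / (1 − d).

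| d | w | r | Chance of a false one-sided positive for surgery, with 155 / 194 analysed per group |
|---|---|---|---|
| 10% | 30% | 18.9% | 8.1% / 8.6% |
| 10% | 40% | 17.8% | 12.6% / 13.9% |
| 20% | 30% | 17.5% | 14.0% / 15.5% |
| 20% | 40% | 15.0% | 31.3% / 36.3% |
| 10% | 10% | 21.1% | bias against surgery |
| 20% | 10% | 22.5% | bias against surgery |

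The nominal level is 5%. Going from 155 to 194 analysed patients does not remove the distortion. It makes a false positive slightly more likely, because a biased difference is estimated more precisely.

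The same holds when there is a true effect. Suppose completers show 20% versus 10% and a fifth of each arm is lost:

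- Lost patients at 10% (nonsurgical) and 30% (surgical): 0.8 × 20 + 0.2 × 10 = 18% versus 0.8 × 10 + 0.2 × 30 = 14%, a difference of 4 points.
- Lost patients at 30% and 5%: 0.8 × 20 + 0.2 × 30 = 22% versus 0.8 × 10 + 0.2 × 5 = 9%, a difference of 13 points.

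The observed 10 points could thus overstate or understate the effect. For scale, 20% of 388 is about 78 patients, while the plan expects 155 × 0.20 + 155 × 0.10 = 46.5 events.

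**The case against.** **Exclusion from the analysis.** A reader might infer that withdrawn patients are excluded, so that the primary analysis becomes per-protocol in all but name and flatly contradicts Section 9. The protocol does not say so. Section 7.5 adds patients and removes none, and both statements can stand if everyone randomised is analysed by allocated arm. The conflict is implied by the purpose given for replacement; it is not stated.

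**Usual-care follow-up.** A reader might also take Section 7.6 to mean that trial outcomes are no longer collected. The text is silent on this. Usual care supplies much of this trial's follow-up: questionnaires at 3, 6 and 12 months are routine (Section 7.1.2), care for revision is estimated from patient charts (Section 7.1.3), and no extra visits are required (Section 10.4). The data are probably obtainable. What is missing is a commitment to obtain and use them.

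**Who withdraws and who replaces.** Nothing defines declining DAIR, or having surgery in the nonsurgical arm, as withdrawal; Sections 4 and 7.3 foresee later DAIR in that arm. Nor does anything say that replacements are chosen for compliance or placed in the vacated arm.

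**Cause of the bias.** The distortion illustrated in the working comes from missing outcomes and would arise without replacement. This is correct. The fault of Section 7.5 is that it treats new patients as a remedy for that loss.

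**Matters for the analysis plan.** Analysis sets and missing-data handling may be left to a statistical analysis plan, which is not at hand, and their absence is not criticised here. Replacement and follow-up, however, are conduct rules fixed in the protocol, and no later plan can restore an outcome that was never collected.

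**Conclusion.** The point holds in a limited form and should be fixed. The double allowance is explicit in Section 7.5 and confirmed by arithmetic. The 20% inflation alone leaves 155 per group, and replacement leaves the number randomised anywhere from 388 to about 486, depending on a rule that is not given. The figures 155, 194 and 388 are not themselves in error, given the one-sided level in Section 9.

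The tension with intention to treat is real but implied. It disappears if every randomised patient stays in the allocated arm with the one-year endpoint ascertained. The protocol permits informative loss of outcomes, but it does not show that such loss will occur, and it gives no basis for computing its direction or size. The false-positive range of about 8% to 36% and the 4-point and 13-point differences rest entirely on assumed withdrawal rates and risks, and on the outcomes of withdrawn patients being left out.

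**What to change.** - **Section 7.5:** delete replacement and state that 388 patients are randomised.
- **Section 7.6:** separate stopping the allocated treatment from leaving the study. State that every randomised patient remains in the allocated arm for analysis, and that one-year revision-for-PJI status is obtained from the hospital chart unless the patient withdraws consent to the use of data.
- **National implant register (LROI):** use it, if at all, only to detect that a revision took place; the chart decides whether it was for PJI. Section 1 cites a Danish study with at least 40% under-reporting of infection as the reason for revision, and expects underestimation in the Dutch register too, "despite its completeness of over 97" per cent. Completeness for revisions is therefore not completeness for their cause.

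The cost is protocol wording, one line in the consent form on chart and register look-up, and chart checks for withdrawn patients. No additional patients or visits are needed. Charts are already a source for revision care (Section 7.1.3), and Section 10.2 already foresees permission to use the data of patients who are not randomised.
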